7.8. Efficacy Endpoints

Relevant data supporting efficacy analyses will be listed by patient within alvocidib dose level.

7.8.1. Remission Rates

The primary efficacy endpoint is CR rate as assessed by the investigator following treatment with alvocidib. Patients who, for any reason, do not supply bone marrow for response assessment are counted among those not achieving remission.

Summary statistics will include the number and percentage of patients rated as not achieving CR due to not providing a bone marrow biopsy/aspirate, proportion of patients who achieve a CR and exact 95% CI estimated without stratification. Between—treatment-arm statistics will include the Mantel-Haenszel odds ratio and 95% CI estimated with stratification.

A standard logistic regression (LR) model will be estimated relating the probability of achieving CR as a function of baseline MCL-1 dependence. Results will be presented graphically as follows. Patients will be divided into groups according to which range of values their baseline MCL-1 dependence falls:

$$(0\%-\leq d_1), (d_1-\leq d_2), (d_2-\leq d_3), \dots, (d_8-\leq d_9), (d_9-100\%)$$

where $d_1,...,d_9$ are deciles for baseline MCL-1 dependence regardless of treatment arm. Empirical CR rates will be calculated for patients within each range and plotted alongside CR probabilities estimated from the LR model.

Other remission rates (e.g., combined CR rate and combined remission rate) will be summarized similar to CR rate.

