11.3.2 Efficacy Analyses

Objective response to treatment will be determined using the remission definitions detailed in the 2017 European LeukemiaNet Recommendations in AML [10] after Induction/Reinduction (for those patients not achieving a CR after Cycle 1) (see [Appendix E](#)).

- CR_{MRD-} = CR without MRD
- CR = Complete Remission (including patients with morphologic CR who are MRD+ and cytogenetic and/or molecular marker positive)
- CR_i = CR with incomplete hematologic recovery
- MLFS = Morphologic leukemia-free state
- PR = Partial Remission
- SD = Stable Disease
- PD = Progressive Disease

The numbers of overall complete remissions (patients with a best objective response of CR_{MRD}, CR, CR_i or MLFS), and overall remissions (patients with a best objective response of CR_{MRD}, CR, CR_i, MLFS or PR) will be summarized by observed rates and estimated 95% CIs. If there are sufficient numbers of patients achieving remissions for an analysis to be informative, logistic regression will be used to model the probability of achieving a remission as a function of the total alvocidib daily dose level (bolus dose amount + infusion dose amount) and biomarker prediction endpoints (eg, MRD).

Kaplan-Meier time-to-event analyses will be conducted on overall survival, relapse-free survival and duration of remission. Mortality (all causes) at 30 and 60 days will also be calculated. Cox proportional hazards models will be fit to these time-to-event endpoints with the total alvocidib daily dose level (bolus dose amount + infusion dose amount) and biomarker prediction endpoints (eg, MRD) serving as independent variables in the model.

Additional exploratory analyses may be performed to assist the sponsor in planning future studies.

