30- and 60-day survival, adverse events, time to neutrophil recovery, time to platelet recovery, prevalence of tumor lysis syndrome, clinical laboratory parameters, vital signs

Statistical Methods:

Descriptive statistics (including 95% confidence intervals) within and across alvocidib dose levels

2. Abbreviations

Standard abbreviations (e.g., AML = acute myeloid leukemia and mg = milligrams) are omitted intentionally.

AE Adverse Event

AML Acute Myeloid Leukemia
ANC Absolute Neutrophil Count

ATC Anatomical and Therapeutic Class

AUC Area Under Curve

BM Bone Marrow

BSA Body Surface Area
Cl Confidence Interval

CM Ara-C (Cytarabine) and Mitoxantrone

CMH Cochran-Mantel-Haenszel (test)

CR Complete Remission

CRi Complete Remission with Incomplete Blood Count Recovery

CTCAE Common Terminology Criteria for Adverse Events

DDE Drug Dictionary Enhanced

DLT Dose-Limiting Toxicity

DSMB (Independent) Data Safety Monitoring Board

ECOG Eastern Cooperative Oncology Group (performance status)

ELN European LeukemiaNet

HiDAC High-Dose Cytarabine

HR Hazards Ratio

ITT Intent-to-Treat (patient population)

IWG International Working Group

KM Kaplan-Meier (survivor function estimate)

LR Logistic Regression

MedDRA Medical Dictionary for Regulatory Activities

MRD- Minimal Residual Disease Negative

MTD Maximum Tolerated Dose

OS Overall Survival

PBSC Peripheral Blood Stem Cells
PFS Progression-Free Survival

PH Proportional Hazards (model)

PR Partial Remission

PT (MedDRA) Preferred Term

RFS Relapse-Free Survival

ROC Receiver Operating Characteristic (curve)

SAE Serious Adverse Event SAP Statistical Analysis Plan

SCT Stem Cell Transplant/Transplantation

SMQ Standardized MedDRA Query

SOC (MedDRA) System Organ Class

TEAE Treatment Emergent Adverse Event

TLS Tumor Lysis Syndrome

WHO World Health Organization

3. Definitions

Standard statistical terminology (e.g., type-1 error rate and significance level) is omitted intentionally. Efficacy endpoints are defined in Section 4.1 below (see Table 1).

Baseline Value: last measured value prior to the first dose of study drug

Combined CR: response assessment of CR or CRi

Combined Remission: response assessment of CR, CRi or PR

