4.2. Statistical Objectives

The statistical objectives are threefold:

- 1. To define a maximum tolerated dose of alvocidib administered with cytarabine and daunorubicin in newly diagnosed AML patients
- 2. To describe the safety and efficacy of alvocidib administered with cytarabine and daunorubicin in newly diagnosed AML patients

3. To model the relationship between baseline MCL-1 dependence and response to treatment with alvocidib administered with cytarabine and daunorubicin

5. Sample Size

The sample size for this study is not predetermined. The number of patients enrolled depends on the occurrence and pattern of DLTs.

6. Treatment Assignment

Cohorts of 3 patients are assigned a dose of alvocidib according to standard 3+3 dose escalation/de-escalation rules. All patients receive the same, standard doses of cytarabine and daunorubicin.

7. Statistical Methods

Analyses will be performed using SAS statistical software. Default estimation methods in version 9.4 of SAS are always used unless an alternative is specified below. Data summaries will include the mean, standard deviation, median, minimum and maximum values for continuous data; the median, 25th and 75th percentiles, minimum and maximum values for time-to-event endpoints; and the number and percentage of patients in each category for categorical data. Pointwise 95% confidence intervals (CI) will also be estimated for the mean (continuous data), median (time-to-event endpoints) or percentage of patients (categorical data).

In general, data values will be obtained directly from the clinical database (e.g., birth date, treatment dates, AML relapse date and death date). Derivations for certain values not collected explicitly in the database are explained in relevant sections below (e.g., age and treatment failure date, sections 7.6 and 7.8.2, respectively). In some instances, it is beyond the scope of this SAP to explain schemes for patient classifications and data derivations (e.g., classifying patients in cytogenetic risk group according to published criteria). These details will be expounded in the clinical study report.

Durations of time expressed in months (e.g., times-to-event endpoints) will be reported in proportional "months" according to the formula

months =
$$\frac{12}{365.25} \times \text{days}$$

Baseline value of a characteristic is defined as the last measured value prior to the first dose of study drug.

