7.1. Analysis Populations

The intent-to-treat (ITT) patient population includes all patients enrolled in the study regardless of whether they actually received study drug and regardless of whether evidence is found indicating they failed to meet study inclusion/exclusion criteria or had other protocol violations. When the ITT patient population is analyzed, patients are grouped according to their assigned alvocidib dose regardless of actual dose received. The ITT patient population is the analysis population for the primary analyses of efficacy endpoints.

The safety patient population is the subset of ITT patients who received at least one dose of study drug. When the safety patient population is analyzed, patients are grouped according to the actual alvocidib dose received. The safety patient population is the analysis population for all analyses of safety data.

The per-protocol patient population is the subset of safety patients who either (a) have at least one response assessment on study, or (b) die prior to their first scheduled response assessment. However, patients are excluded from the per-protocol patient population if they have an important protocol deviation, such as when evidence is found indicating they failed to meet any study inclusion/exclusion criterion. When the per-protocol patient population is analyzed, patients are grouped according to their assigned alvocidib dose regardless of actual dose received. The per-protocol population is used for sensitivity (secondary, supportive) analyses of efficacy endpoints.

Each of the patient populations listed above may be further subdivided for certain analyses (e.g., by age, race or gender) to assess whether certain subpopulations benefited from treatment with alvocidib more than others or if certain subgroups experienced greater toxicity from exposure to alvocidib.

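### The SAP asks for a stratified between-arm odds ratio for CR without defining arms or strata, and omits the protocol's dose models without explanation, leaving only descriptive CR rates by dose level

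*SAP*

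**What the plan says.** SAP 7.8.1 makes investigator-assessed CR rate the primary efficacy endpoint. It plans the "proportion of patients who achieve a CR and exact 95% CI estimated without stratification", and then between-arm statistics that include the "Mantel-Haenszel odds ratio and 95% CI estimated with stratification". Other remission rates are to be summarised in the same way. The only regression model in that section is a logistic one "relating the probability of achieving CR as a function of baseline MCL-1 dependence". SAP 7.9 repeats a logistic model on MCL-1 dependence alone.

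SAP section 6 (Treatment Assignment) describes the groups: "Cohorts of 3 patients are assigned a dose of alvocidib according to standard 3+3 dose escalation/de-escalation rules". All patients receive the same cytarabine and daunorubicin. The SAP synopsis gives the general method as "Descriptive statistics (including 95% confidence intervals) within and across alvocidib dose levels", and SAP 7.1 states that in ITT analyses "patients are grouped according to their assigned alvocidib dose regardless of actual dose received".

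Protocol 11.3.2 plans more. It states that "logistic regression will be used to model the probability of achieving a remission as a function of the total alvocidib daily dose level", with biomarkers as further predictors. That model is subject to a condition: "If there are sufficient numbers of patients achieving remissions for an analysis to be informative". The same section also plans Cox models for overall survival, relapse-free survival and duration of remission, with total daily dose and biomarkers as covariates. The sufficiency condition is attached to the logistic model only. Protocol section 11 leaves the complete details of the analysis to the SAP.

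**The concern.** A stratified Mantel-Haenszel estimate needs two named groups and named strata. This trial has neither a control arm nor randomisation, and no stratification factor appears in either document. A programmer would have to choose the comparison, the reference group and the strata once the data are in hand, and for the SAP's primary efficacy endpoint. Because the other remission rates follow the same pattern, the gap carries over to them.

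The protocol's model-based description of how remission and survival vary with dose has also disappeared, with no reason given. The SAP lists abbreviations for a hazards ratio and a proportional hazards model, yet no Cox analysis appears in its methods or in its planned tables. At stake is how well the trial can describe activity across the doses it studied.

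**Working it through.** **Figures in the plan.** Neither document gives a figure for the odds ratio or for the dose models. The only design figure is the ceiling of 40 patients in protocol 11.2. The scenario given there adds to 3 + 3 + 6 + 3 + 20 = 35, which lies under that ceiling. It is used here only for group sizes.

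**Inputs.**
- Total daily doses (protocol Table 3): 20+30 = 50, 30+40 = 70, 30+50 = 80 and 30+60 = 90 mg/m².
- Group sizes: 3/3/3/13 (SAP Appendix 2 sample table, N = 22); 3/3/26/3 (protocol 11.2 scenario, N = 35); 3/3/3/26 (same total, with the expansion at the top level).
- CR rates of 46% and 70%: an assumption. They are the rates for 7+3 and for alvocidib with cytarabine and mitoxantrone in the randomised study described in protocol 2.6.2. The regimens differ from the one studied here. Wider ranges are shown for the dose model.

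**Step 1: the odds ratio, with dose level read as arm.** Four dose levels give 6 possible pairs. With no strata, the Mantel-Haenszel estimate Σ(ad/n) / Σ(bc/n) reduces to the crude ad/bc. It is 0, infinite or undefined whenever a cell is zero, which happens when all or none of a group respond. For a group of size n this has probability q(n) = pⁿ + (1−p)ⁿ. For two groups with a common rate p, P = 1 − (1 − q(n₁))(1 − q(n₂)).

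- 3 versus 3, p = 0.46: q(3) = 0.0973 + 0.1575 = 0.2548; P = 1 − 0.7452² = 0.445 (44% from the unrounded 0.4447).
- 3 versus 3, p = 0.70: q(3) = 0.343 + 0.027 = 0.370; P = 1 − 0.63² = 0.603.
- 3 versus 13, p = 0.46: P = 0.255. With p = 0.70: q(13) = 0.0097; P = 1 − 0.63 × 0.9903 = 0.376.
- The minimum in this range is at p = 0.50: 0.4375 for 3 versus 3 and 0.250 for 3 versus 13.
- Two invented strata (1+2 versus 6+7 patients) do not help: 0.265 at p = 0.46 and 0.403 at p = 0.70.

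**Step 2: what remains in the SAP.** Exact (Clopper-Pearson) 95% intervals for CR by dose level:

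| Responders | 95% interval |
|---|---|
| 0/3 | 0% to 71% |
| 1/3 | 1% to 91% |
| 2/3 | 9% to 99% |
| 3/3 | 29% to 100% |
| 6/13 | 19% to 75% |
| 9/13 | 39% to 91% |

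**Step 3: what the protocol's logistic model would add.** Power was computed for an exact conditional trend test. The statistic is the sum of dose × number of responders, given the total number of responders, at two-sided 0.05 (an assumption). CR rates rise linearly on the logit scale from the lowest to the highest dose.

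| CR, lowest to highest dose | 3/3/3/13 | 3/3/26/3 | 3/3/3/26 |
|---|---|---|---|
| 46% to 70% | 9% | 8% | 12% |
| 30% to 80% | 33% | 26% | 42% |
| 20% to 90% | 64% | 55% | 76% |

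Across these layouts, and with a flat 46% rate as well, the chance of separation or no usable slope is 0.3% to 8%. The model can therefore usually be fitted, but it has little power unless the gradient is steep.

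**The case against.** Several points on the other side are sound.

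- A reader might infer that a single-arm trial can produce no odds ratio at all. That goes too far. There are four dose groups, and protocol 11.3.3 itself uses between-arm wording where only dose levels exist. An odds ratio between two dose levels is computable; what is missing is the definition of groups, reference and strata.
- A reader might infer that no analysis of CR by dose survives. The synopsis, 7.1 and 7.8.1 of the SAP together still give the CR rate with an exact interval by assigned dose. Only the model-based analysis is missing.
- The protocol's logistic model was conditional on enough remissions and concerned remission in general, not CR alone. Protocol 7.2 says that a formal efficacy analysis is not appropriate in this study.
- The 3-versus-3 figure is the worst case. A level may hold up to 6 patients, and the MTD level up to 20 more; 3 versus 13 gives the lower figures in Step 1.
- Restoring the model buys little power.

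All of this limits the size of the point. It does not supply the missing definitions or explain why analyses planned in the protocol are absent from the document that is meant to hold the full details.

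**Conclusion.** The point holds as a specification fault in the SAP. The stratified odds ratio cannot be carried out as written. On the most generous reading it fails to give a finite, non-zero estimate in roughly a quarter to three-fifths of cases. That size rests on assumed, equal CR rates of 46% to 70% and on group sizes of 3 versus 3 or 3 versus 13. Separately, the conditional logistic dose model and the Cox dose models of protocol 11.3.2 are omitted without explanation, and the descriptive rates that remain are very imprecise at n = 3.

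Two further inferences are tempting and are not supported. Nothing in the documents shows that the odds ratio was put in place of the dose model. Nor do they say that the recommended phase 2 dose, a secondary objective, depends on a dose-activity model: dose selection as described rests on DLTs and the MTD. The SAP's reference to mitoxantrone as a study drug and the TPI-ALV-201 footers suggest text carried over from another plan, but that is an inference.

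**What to change.** 1. Delete the Mantel-Haenszel sentence in SAP 7.8.1, and replace 'treatment arm' with 'alvocidib dose level' in SAP 4.1, 7.8.1, 7.9 and 7.10.1.
2. Restore the logistic model of protocol 11.3.2 for remission, including CR, with total daily dose as one continuous term and with the protocol's sufficiency condition. Use Firth or exact estimation if cells are sparse. State which remission outcomes are modelled, because the protocol's overall categories count MLFS and the SAP's combined categories do not. State also whether biomarkers enter the same model.
3. Restore the Cox models with dose for overall survival, relapse-free survival and remission duration.
4. Label all of these exploratory, and report each dose effect as an estimate with a 95% interval, not as a test. If the sponsor prefers not to run a model, the SAP should say so and give the reason.

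The cost is SAP wording and a small amount of exploratory programming. No change to conduct, data collection or sample size is needed. The downside is a few more low-power estimates, which the labelling in item 4 addresses.

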11.2 Sample Size

Given the design and primary objectives of this study, the sample size will be determined by the guidelines governing dose escalation/de-escalation and the identification of DLTs. As a result, the final sample size is not fixed and will not be determined by consideration of inferential analyses conducted via statistical hypothesis testing. It may be anticipated that the study sample size will be up to 40 patients. This is based on observing DLTs in 2 of 3 patients enrolled at the fourth dose level (Cohort 4) and declaring the third dose level as the MTD (3 patients each in the first and second dose levels, 6 patients in the third dose level during dose escalation, 3 patients at the fourth dose level, and an additional 20 patients at the third dose level for confirmation of safety as well as additional safety analysis and feasibility for determining MRD by dual methods [ie, MPFC and NGS] at a central laboratory). However, the actual number of patient enrolled may be slightly more or less depending on the actual pattern and frequency of DLTs.

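### Ordinary logistic regression in the exploratory MCL-1 models overstates the log-odds by about 10-20% on average at 35-40 patients, and the ten-group plot is too sparse to show fit

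*SAP*

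**What the plan says.** SAP 4.2 lists three statistical objectives. The third is: "To model the relationship between baseline MCL-1 dependence and response to treatment with alvocidib administered with cytarabine and daunorubicin". SAP 7.8.1 gives the method: "A standard logistic regression (LR) model will be estimated relating the probability of achieving CR as a function of baseline MCL-1 dependence". SAP section 7 sets the estimation rule: "Default estimation methods in version 9.4 of SAS are always used unless an alternative is specified below". Neither 7.8.1 nor 7.9 names an alternative for this model.

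For display, 7.8.1 cuts patients into ten groups at nine points that "are deciles for baseline MCL-1 dependence regardless of treatment arm", and adds: "Empirical CR rates will be calculated for patients within each range and plotted alongside CR probabilities estimated from the LR model". SAP 7.9 fits the CR model again, adds an ROC AUC with a jackknife interval as the measure of how well the marker predicts CR, and extends these analyses to combined CR and combined remission.

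On size, SAP section 5 says "The sample size for this study is not predetermined", while Protocol 11.2 says "It may be anticipated that the study sample size will be up to 40 patients". Protocol section 3 places MCL-1 under exploratory objectives. Protocol 11.3.3 fits the model only if enough patients reach remission to make it informative; SAP 7.8.1 and 7.9 do not repeat that condition.

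**The concern.** ML logistic slopes are biased away from zero in small samples, and no finite estimate exists when the marker separates the two outcomes completely. What matters is the size of the scarcer outcome group, not the total. If about 70% of patients reach CR, the scarce group is the failures, whereas the protocol's condition counts remissions. Combined CR and combined remission include every CR patient, so they cannot have more failures than CR and may have fewer.

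The plot has a related weakness. A group of two to four patients can show only a few possible rates, so points will scatter widely around even a correct curve. The reported odds ratio would tend to look stronger than the truth, beside a figure that can neither support nor contradict it.

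**Working it through.** **1. Sample size.** Protocol 11.2 itemises "3 patients each in the first and second dose levels, 6 patients in the third dose level during dose escalation", then 3 at the fourth level and 20 in the expansion: 3 + 3 + 6 + 3 + 20 = 35. This fits under the ceiling of 40 but does not add up to it, so I used 35 and 40. I also used 22, the total in the sample table of SAP Appendix 2, as a low case only.

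**2. Response rate (assumed).** Protocol 2.6.2 reports 70% and 46% CR in the two arms of a prior randomised study, and 2.7 reports 74% for the hybrid schedule. Expected patients without CR, N × (1 − CR rate):

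| N | CR 70% | CR 74% |
|---|---|---|
| 22 | 6.6 | 5.7 |
| 35 | 10.5 | 9.1 |
| 40 | 12.0 | 10.4 |

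At 46% the scarcer group is the remissions: 22 × 0.46 = 10.1, 35 × 0.46 = 16.1, 40 × 0.46 = 18.4.

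**3. Marker and effect (assumed; the documents give neither).** Standard normal marker z, with odds ratios of 1.5 to 4 per SD (log-odds ln 1.5 = 0.41 to ln 4 = 1.39). The precision runs in step 5 go up to 1.5.

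**4. Bias.** The model is logit P(CR) = α + βz, with α set to give the stated CR rate. Relative bias is mean(β̂)/β − 1 over non-separated samples, with 10,000 simulated trials per setting. Ranges are across CR 46-74% and the odds ratios above.

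| N | Mean, ML | Median, ML | Separation |
|---|---|---|---|
| 22 | +22 to +40% | +8 to +14% | at most 2.3% |
| 35 | +13 to +21% | +5 to +9% | at most 0.1% |
| 40 | +11 to +17% | +4 to +7% | at most 0.1% |

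At N=22 the mean is 29-40% for CR 70-74% and 22-33% for CR 46-60%. Firth's penalised likelihood had mean bias of −1% to +4% throughout. A right-skewed marker at odds ratio 2 and CR 70% raises the ML figures to 44%, 22% and 17% at N = 22, 35 and 40.

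**5. Spread.** For a true odds ratio of 2 at CR 70%, the central 95% of ML estimates runs 0.72-21 (N=22), 0.91-8.0 (N=35) and 1.0-6.6 (N=40). Root mean squared error (RMSE) at CR 70%, 3,000 trials per setting, for log-odds 0.7 / 1.0 / 1.5:

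| N | ML | Firth |
|---|---|---|
| 35 | 0.55 / 0.69 / 1.05 | 0.47 / 0.52 / 0.70 |
| 40 | 0.48 / 0.58 / 0.86 | 0.41 / 0.48 / 0.64 |

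At N=35 and log-odds 1.0, ML's mean bias is 15%, or 0.15. Its share of mean squared error is 0.15² / 0.69² = 0.0225 / 0.476, about 5%.

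**6. Combined endpoints.** With an assumed 85% rate, which the documents do not give, mean overstatement is about 22-35% at 35-40 patients. A second run of 4,000 trials per setting gave 17-30%, because a few extreme fits drive the mean. Separation in that run was 0.1-2.5%.

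**7. Decile groups.** N=22 gives 2-3 patients per group and N=35 gives 3-4. N=40 averages 4 (3-5 depending on the quantile rule). Exact (Clopper-Pearson) 95% intervals: 1/2 gives 1-99%, 2/3 gives 9-99%, 2/4 gives 7-93%.

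**The case against.** The strongest reply is that this is a descriptive, exploratory analysis in a phase 1 trial, and that sample size limits it far more than the estimator does. That stands: bias is about 5% of mean squared error in step 5, and Firth does not turn a small sample into an informative one. It does lower RMSE as well as bias, however, so the reply is not a reason to keep ML.

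A reader might infer that the slope is the trial's answer on whether MCL-1 dependence predicts remission. The documents do not support that. SAP 7.9 and Protocol 11.3.3 give that role to the ROC AUC, which for the raw marker depends only on ranks and would be the same under Firth. Nor do the documents say that the slope will select biomarkers for later trials.

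A reader might also take 30-40% as the bias at this trial's size. That needs 22 patients and a CR rate of about 70% or more. The SAP's table with 22 is a layout sample covering patients enrolled under Amendments 2-4, with 8 of 22 withdrawal reasons missing, while the SAP is written to Amendment 6.

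The protocol's condition on fitting the model is a partial safeguard, and the SAP calls the protocol its companion. But the condition counts remissions and sets no threshold.

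On the plot, 7.8.1 plans a display and not a formal calibration test, and tertiles would be imprecise too: 5/7 gives 29-96% and 8/12 gives 35-90%. Both points are fair, and they favour showing individual patients over another grouping.

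**Conclusion.** The point holds at a moderate size. At the protocol's 35-40 patients, ordinary ML would overstate the MCL-1 log-odds by about 10-20% on average; with only 22 analysed, by about 20-40%. The typical (median) overstatement is smaller, about 4-14% across these sizes. Separation is unlikely for CR itself and becomes a practical possibility only if a combined endpoint has a much higher rate. The decile plot cannot show fit or misfit at any of these sizes.

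These figures rest on an assumed normal marker, an assumed effect of about 0.4-1.5 per SD, and CR rates borrowed from prior studies. A skewed marker, a higher remission rate or missing baseline MCL-1 samples would make the bias larger; the documents give no missing rate. This is a cheap improvement, and it does not affect the trial's dose-finding conclusions.

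**What to change.** In SAP 7.8.1 and 7.9, fit the MCL-1 logistic models for CR, combined CR and combined remission with the FIRTH option in PROC LOGISTIC, and report profile-penalised 95% confidence intervals. Estimates then stay finite under separation, for which the SAP has no rule.

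Replace the decile display with the fitted curve and its confidence band over individual patient outcomes. Tertiles with exact intervals are an acceptable alternative if the text says that they are wide. Leave the raw-marker ROC AUC of SAP 7.9 as the measure of predictive ability.

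The cost is one procedure option and one redrawn figure. No new data are needed, and neither enrolment nor patient care changes. The one statistical downside is that Firth's fitted probabilities shrink slightly toward 50%; a standard intercept correction removes this and should be applied to the plotted curve.
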